Subject Incidence: A subject counts once for each preferred term. Percentages use the number of treated subjects as the denominator.

a Note that rash maculopapular and rash macular represent the 2 most common terms used to describe rash.

As of 27 March 2013, there are 5 studies actively enrolling patients with multiple myeloma to investigate oral ixazomib in combination with standard combination regimens. The most frequent (at least 10%) AEs occurring in the pooled safety population from Studies C16005, C16006, C16008, and C16013 are shown for all grades (Table 3). Note that in combination trials, related is defined as related to any study drug in the combination regimen.

Table 3-3 Most Common (At Least 10% of Total) Treatment-Emergent Adverse Events in Oral Combination Studies

| Primary System Organ Class Preferred Term | Total Oral Combo Agent (5/6/8/13) | |
|--|--------------------------------------|-------|
| | n = 173 | n (%) |
| | | |
| Subjects with at Least One Adverse Event | 163 (94) | |
| Gastrointestinal disorders | 139 (80) | |
| Nausea | 65 (38) | |

Table 3-3 Most Common (At Least 10% of Total) Treatment-Emergent Adverse Events in Oral Combination Studies

| Primary System Organ Class Preferred Term | Total Oral Combo Agent (5/6/8/13) |
|--|--------------------------------------|
| | n = 173 |
| | n (%) |
| Diarrhoea | 81 (47) |
| Vomiting | 51 (29) |
| Constipation | 57 (33) |
| General disorders and administration site conditions | 132 (76) |
| Fatigue | 76 (44) |
| Pyrexia | 39 (23) |
| Oedema peripheral | 61 (35) |
| Asthenia | 20 (12) |
| Nervous system disorders | 115 (66) |
| Headache | 28 (16) |
| Dizziness | 34 (20) |
| Neuropathy peripheral | 45 (26) |
| Metabolism and nutrition disorders | 91 (53) |
| Decreased appetite | 25 (14) |
| Hypokalaemia | 34 (20) |
| Blood and lymphatic system disorders | 88 (51) |
| Thrombocytopenia | 49 (28) |
| Anaemia | 45 (26) |
| Neutropenia | 43 (25) |
| Lymphopenia | 20 (12) |
| Skin and subcutaneous tissue disorders | 102 (59) |
| Rash maculopapular ^a | 29 (17) |
| Rash macular ^a | 22 (13) |
| Musculoskeletal and connective tissue disorders | 99 (57) |
| Back pain | 42 (24) |
| Pain in extremity | 31 (18) |
| Arthralgia | 22 (13) |
| Respiratory, thoracic and mediastinal disorders | 80 (46) |
| Cough | 36 (21) |
| Dyspnoea | 26 (15) |
| Infections and infestations | 92 (53) |
| Upper respiratory tract infection | 35 (20) |

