2. STUDY OBJECTIVES

2.1 Primary Objectives

Specific Aim 1. To determine the safety and efficacy of ixazomib as a desensitization strategy. 10 highly sensitized kidney transplant candidates on the waitlist for more than 24 months will receive ixazomib 3 mg (and dexamethasone 20 mg) on days 1, 8, and 15 of a 28 cycle for 12 months. The primary objective is to evaluate the safety (distal neuropathy, thrombocytopenia, and gastrointestinal symptoms) and efficacy (decline in cPRA > 20%) of ixazomib. The secondary efficacy endpoint is transplantation rate within 12 months of therapy.

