3. STUDY ENDPOINTS

3.1 Primary Endpoints (safety and efficacy)

Primary efficacy and safety endpoint:

- Efficacy endpoint: A decline in cPRA > 20%.
- Safety endpoint: infections, malignancies, hematological complications including leucopenia, anemia, and thrombocytopenia, cardiovascular complications and events, distal neuropathy, gastrointestinal symptoms, and immunosuppression-related adverse effects.

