6.2 Study Drug Administration

- Ixazomib and dexamethasone will be taken based on the information in the package insert.
- The starting dose of ixazomib will be 3 mg taken orally on days 1, 8, and 15 of a 28-day cycle. The dose of dexamethasone will be 20 mg taken orally on the same days as ixazomib.
- Patients will take ixazomib and dexamethasone for twelve (12) 28-day cycles.
- Ixazomib should be taken once a week on the same day and at approximately the same time for the first three weeks of a four week cycle. Ixazomib should be taken at least one hour before or at least two hours after food. The whole capsule should be swallowed with water. The capsule should not be crushed, chewed or opened. If an ixazomib dose is delayed or missed, the dose should be taken only if the next scheduled dose is ≥ 72 hours away. A missed dose should not be taken within 72 hours of the next scheduled dose. A double dose should not be taken to make up for the missed dose. If vomiting occurs after taking a dose, the patient should not repeat the dose. The patient should resume dosing at the time of the next scheduled dose.
- Ixazomib and dexamethasone should not be taken at the same time, because dexamethasone should be taken with food and ixazomib should not be taken with food.
- Ixazomib and dexamethasone will be dispensed monthly by the PRC
- Diaries/logs will be used by patients to track their doses.

Treatment Plan and Laboratory Assessment. Participants will undergo a 12-month treatment

regimen of ixazomib-dexamethasone on days 1, 8, and 15 of a 28-day cycle, for 12 cycles (Table 1-1 below). The dose of ixazomib (3 mg) is based on packet information for patients with reduced kidney function and will be taken at least one hour before or at least two hours after food. The dose of dexamethasone is 50% lower than the dose recommended in the package insert to reduce the possibility of metabolic complications in ESRD.

Table 1-1 IXADES Treatment Protocol for desensitization

| 28-Day Cycle (a 4-week cycle) | | | | | | | | |
|-------------------------------|--------|----------|--------|-----------|--------|------------|--------|------------|
| | Week 1 | | Week 2 | | Week 3 | | Week 4 | |
| | Day 1 | Days 2-7 | Day 8 | Days 9-14 | Day 15 | Days 16-21 | Day 22 | Days 23-28 |
| Ixazomib (NINLARO) 3 mg | ✓ | | ✓ | | ✓ | | | |
| Dexamethasone 20 mg | ✓ | | ✓ | | ✓ | | | |

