| 
 Delay of > 2 weeks in the start of a subsequent cycle due to lack of toxicity recovery as defined in Section 6.3.1 ANC < $1.0 \times 10^9/L$, platelet count < $75 \times 10^9/L$, or other nonhematologic toxicities > Grade 1 or not to the patient's baseline condition | 
 Hold ixazomib until resolution as per criteria Section 6.3.1. Upon recovery, reduce ixazomib 1 dose level. The maximum delay before treatment should be discontinued will be 3 weeks or at the discretion of the PI. |

Treatment modifications due to ixazomib-related AEs are outlined in Table 4-3.

Table 4-3 **Ixazomib** Treatment Modification (Delays, Reductions, and Discontinuations) Due to Adverse Events (Non-Hematologic Toxicities)

| Adverse Event (Severity) | Action on Study Drug | Further Considerations |
|---|---|---|
| Peripheral Neuropathy: | | |
| Grade 1 peripheral neuropathy | 
 No action | Grade 1 signs and symptoms: asymptomatic; without pain or loss of function; clinical or diagnostic observations only [14] |
| New or worsening Grade 1 peripheral neuropathy with pain or Grade 2 | 
 Hold study drug until resolution to Grade ≤ 1 or baseline | Grade 2 signs and symptoms: Moderate symptoms; limiting instrumental activities of daily living (ADL) [14] |

Table 4-3 Ixazomib Treatment Modification (Delays, Reductions, and Discontinuations) Due to Adverse Events (Non-Hematologic Toxicities)

| Adverse Event (Severity) | Action on Study Drug | Further Considerations |
|--|---|--|
| New or worsening Grade 2 peripheral neuropathy with pain or Grade 3 | 
 Hold study drug until resolution to Grade \leq 1 or baseline Reduce study drug to next lower dose upon recovery | Grade 3 signs and symptoms: severe symptoms; limiting self-care ADL; assistive device indicated [14] |
| New or worsening Grade 4 peripheral neuropathy | 
 Discontinue study drug | |
| Grade 2 Rash | 
 Symptomatic recommendations as per section 6.7 | The investigator and project clinician may discuss considerations for dose modifications and symptom management. |

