8.2 Procedures for Reporting Serious Adverse Events

AEs may be spontaneously reported by the patient and/or in response to an open question from study personnel or revealed by observation, physical examination, or other diagnostic procedures. When possible, signs and symptoms indicating a common underlying pathology should be noted as one comprehensive event. For serious AEs, the investigator must determine both the intensity of the event and the relationship of the event to study drug administration.

AEs which are serious must be reported to Millennium Pharmacovigilance (or designee) from the first dose of study drug through 30 days after administration of the last dose of ixazomib. Any SAE that occurs at any time after completion of ixazomib treatment or after the designated follow-up period that the sponsor-investigator and/or sub-investigator considers to be related to any study drug must be reported to Millennium Pharmacovigilance (or designee). In addition, new primary malignancies that occur during the follow-up periods must be reported, regardless of causality to study regimen, up to one month after the last dose of the investigational product, starting from the first dose of study drug. All new cases of primary malignancy must be reported to Millennium Pharmacovigilance (or designee).

Planned hospital admissions or surgical procedures for an illness or disease that existed before the patient was enrolled in the trial are not to be considered AEs unless the condition deteriorated in an unexpected manner during the trial (e.g., surgery was performed earlier or later than planned). All SAEs should be monitored until they are resolved or are clearly determined to be due to a patient's stable or chronic condition or intercurrent illness(es).

Since this is an investigator-initiated study, the principal investigator [name], also referred to as the sponsor-investigator, is responsible for reporting serious adverse events (SAEs) to any regulatory agency and to the sponsor- investigator's EC or IRB.

Regardless of expectedness or causality, all SAEs (including serious pretreatment events) must also be reported in English to Millennium Pharmacovigilance (or designee):

Fatal and Life Threatening SAEs within 24 hours of the sponsor-investigator's observation or awareness of the event

All other serious (non-fatal/non life threatening) events within 4 calendar days of the sponsor-investigator's observation or awareness of the event

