9. SAFETY MONITORING

9.1 Safety Monitoring

The investigator is responsible for monitoring the safety of subjects who have enrolled in the study. For this study, adverse events will be solicited from subjects to identify an occurrence or worsening of an unintended sign or symptom, related to the ingestion of the study drug. The study team will ask subjects prior to each cycle if they experienced any new medical related signs or symptoms since taking the study drug. Subjects will be asked about any adverse events they may have experienced again monthly, prior to each cycle, and at the five study visits. Only the adverse events considered related (possibly, probably or definitely) to the ingestion of the study drug will be entered into and managed in the ICTR OnCore system quarterly.

At each visit, subjects will be assessed for AEs by the study team. They will be examined by the principal investigator 5 times (please see tables 2-1 a-b and Figure 1, below): Days 1, 85, 169, 253, and 373 + 6, - 3).

- Day 1: Prior to treatment initiation. H&P, Labs, Bone Marrow Aspirate
- Day 85 + 6, - 3: Prior to treatment dose. H&P, Labs
- Day 169 + 6, - 3 Prior to treatment dose. H&P, Labs
- Day 253 + 6, - 3 Prior to treatment dose. H&P, Labs
- Day 373 + 6, - 3 After treatment completion, H&P, Labs, Bone Marrow Aspirate
- Study drug will be dispensed at each month's in-person visit, prior the initiation of the next cycle, and after reviewing the AEs and monthly labs.

- Patients will undergo monthly CBC and bi-weekly liver function tests (LFTs) for the first three months. After the first 3 months, CBCs and LFTs will be done monthly. cPRA, BAFF/APRIL, DSA and antibodies will be checked every three months (5 times total). Bone marrow aspirates will be collected at the beginning and at one of the following time points: one month (+ 6, - 3 days) after the end of the 12 month study, cPRA<80%, time of transplant, or time of subject withdrawal from the study.
- Additional visits may be required if the subject has to hold treatment and needs to return to the clinic for blood draws to confirm eligibility to continue. Please see Table 4-3, Dose Adjustments for Hematologic Toxicities for dose adjustment plan.

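### Distal neuropathy and GI symptoms are named primary safety outcomes, but the plan specifies no symptom-specific query, graded baseline or neurological examination for them, so mild or slowly worsening events may be missed

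*Combined protocol and SAP*

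**What the plan says.** Section 2.1 states: "The primary objective is to evaluate the safety (distal neuropathy, thrombocytopenia, and gastrointestinal symptoms) and efficacy". Section 3.1 gives a wider list that still contains both outcomes: "Safety endpoint: infections, malignancies, hematological complications including leucopenia, anemia, and thrombocytopenia, cardiovascular complications and events, distal neuropathy, gastrointestinal symptoms". The Study Objectives row of the Protocol Summary makes toxicity a secondary objective instead, but singles out the same three outcomes.

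On background frequency: Table 3-3 in section 1.5 has the row "Neuropathy peripheral | 45 (26", from 173 patients in the combination studies.

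On how events are found:

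- Section 9.1: staff will "ask subjects prior to each cycle if they experienced any new medical related signs or symptoms". The sentence before it says the purpose of asking is to pick up both new and worsening problems. The section also provides for asking at the five examination visits.
- Section 8.2: "AEs may be spontaneously reported by the patient and/or in response to an open question from study personnel". The same sentence adds what staff observe, what an examination shows and what other tests reveal.
- Sections 4.1, 7.1.8 and 9.1: history and physical examination on Days 1, 85, 169, 253 and 373. None states a neurological component.
- Section 6.2: "Diaries/logs will be used by patients to track their doses". No symptom entry is described. The same section measures toxicity by the incidence of adverse events.
- Tables 2-1(a) and (b): a blood count at every cycle start and a general AE Assessment row, with no row for neuropathy or GI symptoms.

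On grading: section 5.2 excludes only Grade 2 or greater neuropathy at entry. Table 4-3 describes the lowest grade thus: "Grade 1 signs and symptoms: asymptomatic; without pain or loss of function; clinical or diagnostic observations only". Its higher rows act on new or worsening neuropathy, and both it and the restart criteria in section 6.3.1 refer to the patient's baseline.

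**The concern.** Of the three safety outcomes singled out in the primary objective, one is measured on a fixed schedule by a laboratory test. The other two depend on whether a patient mentions a symptom when asked a general question, or whether an examiner happens to look for it.

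The gap is in standardisation. Grade 1 neuropathy, as Table 4-3 describes it, is a finding on examination, so a question about symptoms cannot detect it. Slow worsening from an existing Grade 1 can be recognised only against a recorded starting grade. GI symptoms after a dose may have passed by the time the patient is next asked.

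At stake is the descriptive safety result. With 10 patients and no control arm, each missed patient lowers an observed incidence by 10 percentage points (1/10), and the error runs in one direction, toward a conclusion that the drug is well tolerated.

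**Working it through.** **1. Background figures.** These reproduce from Tables 3-2 and 3-3.

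- Peripheral neuropathy: 21/201 = 10.4% (single agent); 45/173 = 26.0% (combination).
- GI disorders, whole organ class: 160/201 = 79.6%; 139/173 = 80.3%.

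They show that the events are common enough to matter. They do not show that events would be missed here.

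**2. Assessment calendar** (Tables 2-1(a) and (b)).

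- AE assessments: 12 cycle starts + Day 323 + Day 373 = 14.
- Cycle starts after Day 1: Days 29, 57, 85, 113, 141, 169, 197, 225, 253, 281 and 309 = 11. Examinations coincide on Days 85, 169 and 253 = 3, so 11 − 3 = 8 restarts have no scheduled examination.
- Doses scheduled before the first on-treatment examination (Day 85): 3 cycles × 3 = 9.
- Recall in Cycle 1 for doses on Days 1, 8 and 15, asked about on Day 29: 28, 21 and 14 days.

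**3. What the grading rules use, against what is specified.**

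| Needed | Specified |
|---|---|
| A starting neuropathy grade, because Grade 1 may enter and the rules refer to baseline | Only that Grade 2 or above is excluded; no recorded 0 or 1 |
| A Day 1 examination | Section 4.1 lists one on Day 1; the footnote to Table 2-1(a) requires it only if not done at screening. These need reconciling |
| A current grade at each restart | A grade is used, but how it is obtained is not stated; no examination at 8 of 11 restarts |
| Detection of asymptomatic Grade 1 | Five examinations, content not stated |

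**4. Illustration of size.** Let p be the true rate and s the share of affected patients who are recorded. The documents give no s; 100%, 75% and 50% are assumptions. P(none recorded in 10) = (1 − p·s)^10.

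| p | s = 100% | s = 75% | s = 50% |
|---|---|---|---|
| 26.0% | 5% | 11% | 25% |
| 10.4% | 33% | 44% | 58% |

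Expected recorded neuropathy cases, 10·p·s, at 26.0%: 2.6, 2.0 and 1.3. For GI disorders at about 80%: 8.0, 6.0 and 4.0, and the chance of recording at least one stays at 99.3% or more throughout. For GI the effect is therefore on the count and the worst grade, not on whether the problem is seen at all.

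**The case against.** The case on the other side is substantial, and it rules out several stronger readings.

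*A reader might infer that an open question is the only route.* It is not. Section 8.2 lists others, there are 14 AE assessments and five examinations with history, and section 4.1 allows examination at unscheduled visits.

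*A reader might infer that worsening is never sought.* Section 9.1 states it as a purpose of asking, and section 8.1.1 counts an increase in severity or frequency as an adverse event. What remains is that the question as worded asks about new problems and has no recorded grade to compare with.

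*A reader might infer that the dose rules lose their trigger.* Asymptomatic Grade 1 carries no action in Table 4-3. The triggers are pain or loss of function, which patients can report.

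*A reader might infer from section 1.10 that neuropathy is not monitored.* Section 9.1 puts it among the data the monitoring committee reviews and calls the section 1.10 areas additional. Section 1.10 itself names nausea, vomiting and diarrhoea.

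The size also rests on assumption. The documents do not say how the rates in Tables 3-2 and 3-3 were collected; if by general questioning, discounting 26% again would count the loss twice. Repeated asking helps: if each inquiry found half of the cases and neuropathy lasted through three inquiries, capture would be 1 − 0.5³ = 87.5% and P(0 of 10) = (1 − 0.26 × 0.875)^10 = 7.6%, not 25%. The rates come from patients with cancer or amyloidosis at various doses, and the 26% from combination regimens. All of this stands.

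Finally, section 7.1 tests discontinuation for adverse events, which depends little on mild symptoms. That stands too. However, Table 4-3 requires discontinuation for neuropathy only at Grade 4, so that endpoint says little about lower grades. Incidence (sections 6.2 and 7.1.8) is where those grades would show.

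A checklist could exist in the CRF or the safety monitoring plan, which sections 9.4 and 7.1.8 leave to be developed. If so, the protocol needs only to say so.

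**Conclusion.** The point holds in a limited form. Two of the three singled-out safety outcomes lack a symptom-specific query, a graded baseline and a stated examination component. Mild or slowly worsening events may therefore be missed, which would bias reported incidence toward good tolerability.

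It would go too far to say that both outcomes are likely to be undercounted. High background rates do not show poor capture, and the size of any undercount cannot be derived from the documents. The rise in P(0 of 10) from 5% to 25% at a true 26% is an illustration. It rests on two assumptions: that 26% applies to this population, and that as few as half of the affected patients are recorded. The effect on the tested discontinuation endpoint is smaller. The change is worth making because incidence of these outcomes is a stated result and the remedy fits existing visits.

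**What to change.** - In section 9.1 and the AE Assessment row of Tables 2-1(a) and (b), keep the general question and add fixed questions on numbness, tingling or pain in the hands and feet, and on nausea, vomiting and diarrhoea. Ask them pre-dose on Day 1 and at every scheduled AE assessment, and record the CTCAE grade each time, including 0.
- State that the five existing physical examinations include a brief distal sensory check. Reconcile the Day 1 examination in section 4.1 with the footnote to Table 2-1(a).
- Add tick boxes for nausea, vomiting and diarrhoea to the existing dose diary.
- In section 7.1.8, report worst grade and change from Day 1 for each patient.

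Cost: about one CRF page, some diary wording and a few minutes per existing visit, with no new visit. Downside: recorded incidence will be higher, and may be less comparable with Tables 3-2 and 3-3, whose method of ascertainment is not stated. No dose or stopping rule changes.

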1.6 Relapsed and/or Refractory Multiple Myeloma

The early development of ixazomib in patients with RRMM involves 2 studies (C16003 and C16004) with similar objectives, but each investigated 1 of the 2 dosing schedules commonly used with the first-in-class proteasome inhibitor, VELCADE.

Study C16003 is an open-label, dose escalation, phase 1 study of ixazomib dosing on a twice-weekly schedule on Days 1, 4, 8, and 11 of a 21-day cycle in adult patients with RRMM (28, 29). Study C16004 is an open-label, dose escalation, phase 1 study of ixazomib dosing on a weekly schedule on Days 1, 8, and 15 of a 28-day cycle in adults patients with RRMM (30-32). Both studies have now completed enrollment. The DLTs in Study C16003 were rash macular and thrombocytopenia and the DLTs in C16004 were nausea, diarrhea, vomiting, and erythema multiforme.

In the dose escalation component of both studies, patients had multiple myeloma that had relapsed following at least 2 lines of therapy that must have included bortezomib, thalidomide (or lenalidomide), and corticosteroids. In both studies, when the MTD was established, cohorts of patients representing the heterogeneous patient population currently seen in clinical practice were to be enrolled into 1 of 4 expansion cohorts, including a relapsed and refractory cohort, a carfilzomib cohort, a proteasome inhibitor-naïve cohort, and a VELCADE-relapsed cohort. Final study results are currently being analyzed, but preliminary data suggest that ixazomib has anti-tumor activity in heavily pretreated MM patients, with durable responses/disease control, and is generally well tolerated. Please refer to the ixazomib IB and SMA for further information.

1.7 Newly Diagnosed Multiple Myeloma (NDMM)

Multiple research paths are being explored in patients with NDMM with a focus on evaluating ixazomib in combination with agents commonly used across treatment settings. The development of ixazomib in combination with lenalidomide and dexamethasone (LenDex) in patients with NDMM who are transplant eligible or ineligible involves 2 studies (C16005 and C16008) with similar study designs except for a few key differences, namely the schedules of ixazomib and dexamethasone. Ixazomib is also being evaluated in combination with melphalan and prednisone (MP) for patients who are not transplant eligible due to age or coexisting morbidity (in Study C16006).

All 3 studies are phase 1/2, with phase 1 focusing on safety and phase 2 on efficacy (and further characterization of safety). Please refer to the ixazomib IB and SMA for further information.

